Title: Comparison of quality of bone marrow biopsy and patient convenience and pain control by a battery powered drill versus conventional methods in patients with plasma cell disorders

PRINCIPAL INVESTIGATOR:

Name:	[name]		
Institution:	Winship Cancer Institute		
Address:	[name]		
	City: Atlanta	State: Georgia	Zip: 30322
Email:	[contact]	[contact]	[contact]

AIMS

1. Primary endpoint - Assessing the quality and quantity of bone marrow core biopsies.
2. Secondary endpoint –
 - (a) Assessing the nature of pain by established VAS questionnaires.
 - (b) Timing of the actual procedure

BACKGROUND:

Since the introduction of Jamshidi needle in 1971, we have not seen any advances in bone marrow sampling technology (Jamshidi & Swaim, 1971). In 2007, a new battery-powered bone marrow biopsy system was developed by OnControl Vidacare Corporation, Shavano Park, Texas, USA. This technology using a battery-powered drill to operate the needle to gain access to the posterior iliac bone was approved by the United States Food and Drug Administration (FDA) and currently commercially available.

The traditional method for gaining bone marrow involves grinding a needle by hand through a patient's skin and bone.

The oncontrol bone marrow biopsy device consists of a powered driver and biopsy needle set. The lithium battery-powered driver resembles a small hand-held drill and drives a needle into medullary cavity of the top ridge of your rear hip bone (iliac crest) to obtain the soft tissue located in the marrow space . The

needle set consists of two parts: an outer cannula, 11 gauge × 4 inches (102 mm) long; and a bevel-tip inner stylet, used to penetrate the cortex of the bone.

This method is most commonly carried out on the top ridge of the rear hip bone with a patient in the right or left lateral position. Procedure performed under anesthesia (medication that causes numbness), local anesthesia is provided via infiltrating an adequate area of the periosteum. Commonly a skin insertion is made (with a lancet) and the needle is inserted through the skin, once the needle touches the bone the drill is started. During the procedure, you will hear a sound and feel the vibration of the needle. After the powered drill advances the needle into the marrow cavity the inner stylet is removed and the threaded cannula grabs the marrow.

Marrow has both solid and liquid parts. Aspiration is the procedure used to collect the liquid part of the marrow. If the solid portion of the bone is sampled, this is called a biopsy.

In the aspiration, an incision will be made and a needle inserted through the skin. Once the needle touches the bone, the power driver will be started and you may feel some vibration. Within a few seconds, your doctor will stop and take a sample of liquid marrow with a syringe.

For the biopsy, after the aspirate has been collected, the power driver is restarted and, in a matter of seconds, your doctor will capture a sample of the solid marrow

Few randomized controlled trials (RCTs) compared the use of the battery powered bone marrow biopsy system to the traditional manual methods however they have certain limitations. Though the use of a powered drill is justified in selected patients, the results are not uniform. Swords et al reported that powered drill significantly reduces needle insertion pain and procedural time when compared to a manual technique (Swords et al., 2011) delivering similar quality of specimens by both method (Swords et al., 2010). In another RCT by Read et al evaluating hematologists-in-training, they were significantly faster and sampling was superior in quality when performed with the power drill (Reed et al., 2011). In the most recent RCT by Bucher et al, both methods produce similar results. In the absence of using conscious sedation, reported pain during the procedure is lower with the powered drill (Bucher et al., 2013). The limitations with these RCTs included relatively small number of patients, significant heterogeneity in patient population, and inclusion of patients with all indications. At our institution we have adapted to the power drill system and majority of the patients receive conscious sedation (by personal communication). We are proposing to conduct a RCT to identify the optimal procedure in patients with plasma cell disorders undergoing bone marrow biopsy due to technical challenges with concomitant osteoporosis/ osteopenia and ongoing bone loss in this particular set of patients.

PATIENTS AND METHODS:

Design

Prospective randomized control trial in multiple myeloma patients.

Outcomes:

- Bone marrow core biopsy length (in mm) and artifacts assessed by the pathologist blinded for the sample.
- Intensity of Pain as measured via VAS (visual analogue scale) for pain, a 10 point scale.
- Time taken by the procedure measured in seconds.

ELIGIBILITY CRITERIA

All patients with existing plasma cell disorders and no history of psychiatric disorders and can receive conscious sedation are eligible to participate in the trial.

EXCLUSION CRITERIA

Pregnant women are excluded from participating in this study due to the uncertainty in the positioning of pregnant patients for the procedure.

METHODOLOGY

PATIENT IDENTIFICATION:

The patients with plasma cell disorders undergoing bone marrow biopsy procedure at the procedure bay in Winship Cancer Institute will be identified weekly. The list of prospective patients will be shared among the clinical and research team.

SEDATION/ANALGESIA:

The eligible patients would be assessed whether they can receive conscious sedation. Any contraindication to receive conscious sedation will exclude the patients from the study. Standard agents for conscious sedation as approved by the Emory University will be used. Standard personnel who can administer the conscious sedation will be able to perform the sedation and bone marrow biopsy.

APPROACH:

The eligible patients on the day of the procedure will be approached and the study strategy and the procedures are explained to the patients. Informed consent is given to the patients and adequate time is given for the patient and family members to review and make a decision regarding participating in the study. Voluntary patients interested in participating in this non-therapeutic study after signing consents will be randomized to the power drill arm or the traditional (Jamshidi) bone marrow biopsy arm.

RANDOMIZATION:

All the study participants are randomized by using a shuffling card method. 100 cards with predestinated procedure name (50 with traditional and 50 with powered biopsy) printed on them are shuffled and patient is asked to pick one card from the deck and he/she will be placed in the respective group. Every time the card is picked it is not replaced into the deck. This helps us to approximately achieve a balance in number of patients in each of the study groups.

QUESTIONNAIRES:

Patients are asked to fill out the VAS pain questionnaire before the start of the procedure and 30 minutes after the procedure, day 1, day 3, and day 7. Subject will be given a VAS pain scale to score the intensity of the pain. Majority of the patients will return to Winship Cancer Institute in a few weeks to discuss the results of the bone marrow biopsy. Questionnaires will be collected during this visit. In the event that the patient is not returning to Winship, patients will use the return stamped envelope provided on the day of the procedure to return the questionnaires. Patients will be contacted over the phone as a reminder to return the completed the VAS questionnaire if not received during the follow-up clinic visit. For the secondary endpoint of time taken for the procedure, we will use a stopwatch from the beginning to the completion of the procedure (skin to skin)

Variables to be considered during analysis: Sample size, length of procedure, pain intensity before procedure and at different time points after procedure, age, gender and BMI.

Statistical methods: Analyzed using a SAS 9.1 version. Continuous variables like, the bone marrow biopsy length, and time taken for procedure are studied with mean, median, range and standard deviation and compared by two-sample t-test. While the categorical variables, pain is studied with χ^2 or Mann Whitney U test or Fisher's exact test.

DATA SAFETY MONITORING PLAN

The bone marrow drill procedure is done as a SOC at our institution, and we have established the safety of the procedure without any untoward events over the last 3-4 years. We have not proposed an interim analysis for futility or efficacy, taking into consideration that the final results of the study if fully

conducted will not harm a patient. [name] will be the primary responsibility for overseeing the data and the interim analysis.

DATA STORAGE AND PROTECTION

All data will be maintained on the REDCap database supported by the Research and Woodruff Health Sciences IT (RWIT) Division at Emory University.. Access to the server is protected by (firewalls, encryption etc) and all accounts will be password protected.

Confidentiality

Your name, telephone number, social security number, residential and mailing addresses will be collected from your medical record for study related contact. Laboratory results, billing, clinical, radiology, physician, and hospital records will also be collected from your medical record.

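### The protocol does not tie the post-procedure VAS to the biopsy site, so unrelated pain can cost the secondary pain comparison precision

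*Combined protocol and SAP*

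**What the plan says.** AIMS gives secondary endpoint (a) as "Assessing the nature of pain by established VAS questionnaires". The Outcomes list describes it as "Intensity of Pain as measured via VAS (visual analogue scale) for pain, a 10 point scale". QUESTIONNAIRES sets the rating times, "before the start of the procedure and 30 minutes after the procedure, day 1, day 3, and day 7", and adds "Subject will be given a VAS pain scale to score the intensity of the pain". None of these places names a body site, a cause of pain or a recall period. The questionnaire itself is not reproduced.

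The completed forms are handed in at a clinic visit some weeks later or returned by post. No staff member is assigned to explain on days 1, 3 and 7 which pain is meant.

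For the analysis, the variables to be considered include "pain intensity before procedure and at different time points after procedure, age, gender and BMI". The tests named for pain under Statistical methods are chi-squared, Mann-Whitney and Fisher's exact, none of which adjusts for a covariate. No change score or covariate model is specified.

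ELIGIBILITY CRITERIA admits all patients with plasma cell disorders who have no psychiatric history and can be sedated. Neither it nor EXCLUSION CRITERIA restricts existing pain. BACKGROUND justifies the choice of population by "technical challenges with concomitant osteoporosis/ osteopenia and ongoing bone loss in this particular set of patients".

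**The concern.** The pain question here is about the device. The title sets pain control with the drill against conventional methods, and BACKGROUND cites earlier trials for pain at needle insertion or during the procedure. The protocol's own measure carries no such anchor. A patient whose hip is comfortable but who hurts elsewhere could truthfully return a high score on day 3, and that score would count as an outcome of the assigned device.

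Such pain does not depend on allocation. It adds spread to both arms and makes a real difference in site pain harder to detect. The share of the score due to other causes would be expected to rise as site pain settles over the week. A finding of no difference would then be ambiguous: the devices may hurt equally, or the question may not have isolated the pain they cause. An item worded too broadly cannot be narrowed after the forms are filled in.

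**Working it through.** **No figure to reproduce.** The documents give 50 cards per arm (RANDOMIZATION) but no SD, target difference, significance level or power for pain. What follows is illustration, and every input except the 50 per arm is an assumption.

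**Step 1: loss of precision.** Assume score = site pain + other pain, with the two parts independent and other pain distributed alike in both arms. Let k = SD of other pain / SD of site pain.

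- The expected difference between arms in VAS points does not change.
- Its standard error is multiplied by √(1 + k²).
- The standardised difference is multiplied by 1/√(1 + k²).

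| k | SE multiplied by | Standardised effect multiplied by | A 0.5 SD site difference becomes |
|---|---|---|---|
| 0.5 | √1.25 = 1.12 | 0.89 | 0.45 SD |
| 1 | √2 = 1.41 | 0.71 | 0.35 SD |
| 2 | √5 = 2.24 | 0.45 | 0.22 SD |

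**Step 2: the same in power.** Assume a site-pain SD of 2.0 points and two-sided alpha 0.05. Choose the difference that gives 80% power at 50 per arm: 2.0 × √(2/50) × (1.96 + 0.84) = 1.12 points. With other-pain SD s:

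- total SD = √(4 + s²)
- power = Φ(1.12 / (total SD × √(2/50)) − 1.96)
- n per arm for 80% power = 50 × (4 + s²)/4, rounded up

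| s | Total SD | Power, unadjusted | n per arm for 80% | Mann-Whitney power, simulated (3,000 runs) |
|---|---|---|---|---|
| 0 | 2.00 | 80% | 50 | 78% |
| 1 | 2.24 | 71% | 63 | 68% |
| 2 | 2.83 | 51% | 100 | 48% |
| 3 | 3.61 | 34% | 163 | 33% |

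**Step 3: credit for the pre-procedure score.** Suppose the baseline VAS records other pain and correlates ρ with other pain at follow-up. Adjustment leaves residual variance 4 + s²(1 − ρ²).

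| s | Unadjusted | ρ = 0.5 | ρ = 0.7 | ρ = 0.9 |
|---|---|---|---|---|
| 2 | 51% | 56% | 63% | 73% |
| 3 | 34% | 40% | 48% | 65% |

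At equal SDs (k = 1) the factor on the standardised effect is 1/√(1 + (1 − ρ²)). It rises from 0.71 unadjusted to 0.76, 0.81 and 0.92. Adjustment recovers part of the loss, and most of it when other pain is stable over the week. It does not recover all of it.

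**The case against.** Several limits apply, and most of them stand.

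- **The form is not in the documents.** A reader might infer that the VAS asks patients for their pain in general. The protocol only summarises the instrument, and the printed sheet may already name the site. What can be said is that the protocol does not.
- **Using the same VAS beforehand does not prove that it rates general pain.** It is equally consistent with a baseline rating at the planned site. The text leaves this open.
- **Bone loss is not bone pain.** A reader might infer a large burden of disease pain from the osteoporosis and bone loss in BACKGROUND. That passage raises them as technical difficulties for sampling, and no passage mentions bone pain or its variation from day to day. Unrelated pain is a plausible inference in a population with no restriction on existing pain, but its amount could be negligible.
- **It is not bias in favour of a device.** A reader might take shrinkage of the standardised effect to mean a biased difference in VAS points. Under the additive model the expected difference is unchanged, because randomisation balances unrelated pain in expectation. If patients instead rated whichever pain was worst, the difference in points would shrink as well. The documents do not say how patients would combine pains, so the point does not rest on that.
- **A pre-procedure score is collected and listed for analysis.** This is real mitigation, but no method is given for using it and the named tests do not. Keeping one unanchored item and adjusting for baseline is a reasonable alternative. It still leaves in the score the change in other pain over the following 7 days.
- **Pain is a secondary endpoint with no stated power target.** The biopsy-quality endpoint and procedure time are untouched, so a reading that the whole device comparison is weakened goes too far.

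**Conclusion.** The point holds in limited form. As written, the protocol does not restrict the post-procedure VAS to the biopsy site and compares pain with unadjusted tests, so scores from 30 minutes to day 7 can carry pain unrelated to the device. The consequence is lost precision, and a less interpretable null result, for secondary endpoint (a) alone.

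The size cannot be stated from the documents. Under independent, additive pain with assumed SDs, a comparison with 80% power for site pain at 50 per arm would have 71%, 51% or 34% if the other-pain SD were half, equal to or one and a half times the site-pain SD. Using the baseline score would restore part of that. If little unrelated pain is present, or the form already names the site, the loss is small or nil. The change is still worth making because it is cheap and cannot be made after collection.

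**What to change.** Check the form first. If it already names the biopsy site, state that in Outcomes and QUESTIONNAIRES and leave the item as it is. Otherwise:

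1. Word the VAS item at 30 minutes and on days 1, 3 and 7 as pain at the place on the hip where the biopsy was taken, and use that item for secondary endpoint (a).
2. Ask the same item about the planned site before the procedure, so that a baseline on the same scale is kept and change from baseline keeps its meaning.
3. If general pain is also of interest, put it on a separate line that does not enter the device comparison.
4. In Statistical methods, include the pre-procedure score as a covariate in the pain comparison. The tests now named cannot do this, so a baseline-adjusted model has to be specified.

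The cost is a line of wording, ethics approval of the revised form, a sentence in the analysis section, and one extra line for patients if general pain is kept. Neither the procedures nor the number of patients changes.

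### Day 1, 3 and 7 pain forms can go unreturned and the named tests use one value per patient, so loss costs precision and could bias those comparisons; a repeated-measures model would use the ratings already planned.

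*Combined protocol and SAP*

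**What the plan says.** The Questionnaires section of the combined protocol and SAP asks for VAS ratings "before the start of the procedure and 30 minutes after the procedure, day 1, day 3, and day 7". On return of the forms it says "Majority of the patients will return to Winship Cancer Institute in a few weeks to discuss the results" and "Questionnaires will be collected during this visit". For patients who do not come back, "patients will use the return stamped envelope provided on the day of the procedure to return the questionnaires". There is one safeguard, for forms not received at the follow-up visit: "Patients will be contacted over the phone as a reminder to return the completed the VAS questionnaire". The call asks for the paper form; recording a score by phone is not described. The section does not say when the 30-minute form is handed in.

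The Statistical methods paragraph says "pain is studied with χ^2 or Mann Whitney U test or Fisher's exact test". The list of variables just above it includes pain before the procedure and at the later times, with age, gender and BMI, but no model that would use them is named. No expected return rate, missing-data rule, main pain time point or pain sample size is given. The Aims make pain secondary endpoint (a). The Randomization section's card deck implies 50 patients per arm.

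**The concern.** The last three ratings fall after the day of the procedure, and the patient must keep the forms and hand them in or post them. The plan expects some loss, since it provides reminder calls. Each named test takes one value per patient, so the comparison on a given day uses only the patients whose form for that day came back. Their other ratings contribute nothing.

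Two things follow. Any loss reduces precision in a trial of about 100 patients. And if return depends on early pain while the device changes early pain, the patients left at day 3 or day 7 are no longer a randomised comparison. The Background cites a trial in which the drill reduced needle-insertion pain, so an early device effect is plausible. A small, null or reversed later difference could then not be told apart from form loss.

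**Working it through.** The documents give no power calculation, VAS standard deviation, target difference or return rate, so there is no figure to reproduce. From the documents: 50 per arm and four post-procedure ratings. Assumed: SD 2.2 points, two-sided 0.05, equal correlation ρ between ratings, and return rate π of 60% to 90%.

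**Bias at day 3.** Assume ρ = 0.6, a drill benefit of 1.5 points at 30 minutes and 0.5 at day 3, and log-odds of return that change by 1.2 per SD of 30-minute pain, alike in both arms. With equal SDs and return depending only on 30-minute pain:

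observed day-3 difference = 0.5 − ρ × (1.5 − 30-minute difference among returners).

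Large simulations give:

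| Return | Returned forms show | Shortfall | Implied 30-minute difference among returners |
|---|---|---|---|
| 60% to 75% | 0.31 to 0.36 | 0.19 to 0.14 | 1.5 − 0.19/0.6 = 1.18 to 1.5 − 0.14/0.6 = 1.27 |
| 90% | 0.42 | 0.08 | 1.5 − 0.08/0.6 = 1.37 |

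- An estimate that also uses the 30-minute score gives 0.49 to 0.51, against the true 0.5.
- With a link of 0.6 per SD the bias is under 0.1 point. With random loss there is none.
- With 2 points at 30 minutes and no true day-3 difference, the 1.2 link gives a spurious 0.19 to 0.25 points against the drill at 60% to 75% return, and about 0.1 at 90%.

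**Loss that depends on the unseen score.** In SD units, take a true day-7 difference of −0.50 and 75% return. If return depends on the day-7 score alike in both arms, returned forms give −0.44 and an estimate using earlier ratings −0.45 to −0.47. If the dependence runs in opposite directions by arm, the figures are −0.92 to −0.93 and −0.69 to −0.87. The earlier ratings correct this only in part.

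**Power at day 1 for a constant 1-point effect.** Power = Φ(1/SE − 1.96).

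- t-test on returned forms, SE = 2.2 × √(2/(50π)). Full return: SE 0.44, power 62%. π = 0.9: SE 0.464, power 58%. π = 0.6: SE 0.568, power 42%.
- Repeated-measures model without baseline, 30-minute form complete and the later forms lost together: SE² = (2 × 2.2²/50) × [ρ² + (1 − ρ²)/π]. With ρ = 0.4, π = 0.6: 0.1936 × 1.56 = 0.302, SE 0.550, power 44%. With ρ = 0.6, π = 0.9: 0.1936 × 1.071 = 0.207, SE 0.455, power 59% (60% if forms are lost separately by day).
- Adding baseline, if it correlates equally with later scores: multiply 0.1936 by (1 − ρ²) and replace ρ in the bracket by ρ/(1 + ρ). With ρ = 0.4, π = 0.6: 0.1626 × 1.612 = 0.262, SE 0.512, power 50%. With ρ = 0.6, π = 0.9: 0.1239 × 1.096 = 0.136, SE 0.368, power 78%.

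**Average over four ratings, without baseline.** With b = (1 + 3ρ)/4, SE² = 0.1936 × [b² + (b − b²)/π].

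- ρ = 0.6, π = 0.6: b = 0.70, 0.1936 × 0.84 = 0.163, SE 0.403, power 70%.
- ρ = 0.4, π = 0.9: b = 0.55, 0.1936 × 0.5775 = 0.112, SE 0.334, power 85% (86% if forms are lost separately by day).

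**The case against.** **The bias is hypothetical and modest.** It needs return to depend on pain, and the documents give no return rate or link. The 1.2 link is strong: at 60% return it means return running from about 34% to 85% across plus or minus 1 SD of pain. The worst case, about 0.25 points, is less than half the standard error of 0.46 to 0.57 at these return rates. This stands. A reader might infer that the pain result will be biased; the documents support only that it could be.

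**The reminder call addresses this loss.** It should raise return and deserves credit. It still asks for paper, and nothing says what happens when none arrives.

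**The gain in power comes from averaging, not from recovering lost forms.** This also stands. A reader might set 42% to 58% at day 1 beside 70% to 86% for the model and conclude that single-day tests throw away most of the information. Those figures answer different questions, and the second assumes the same effect at every time. At day 1 itself, the model without baseline gives 44% to 60%.

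**Use of the earlier ratings is undescribed, not excluded.** Baseline and later pain are listed as analysis variables. But none of the named tests can use them jointly, so as written they play no part in the comparison.

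**Other comparisons are little affected.** The 30-minute rating is made soon after the procedure and is probably near complete, though that is an inference. Biopsy quality, the primary endpoint, does not depend on these forms.

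**Conclusion.** The point holds for the day 1, 3 and 7 pain comparisons. The plan combines delayed return of forms with tests that use one value per patient, and has no method for missing scores. Loss costs precision for certain: at day 1, under the stated assumptions, power falls from 62% with every form to 58% at 90% return and 42% at 60%. Bias is conditional. It is about 0.14 to 0.19 points on a true 0.5 under a strong link at 60% to 75% return, 0.08 at 90%, under 0.1 with the weaker link, and nil with random loss. All these sizes rest on an assumed SD, correlation and return rate.

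The documents do not support a claim that the pain result is invalid or that the primary endpoint is affected. This is an inexpensive improvement to a secondary analysis, and worth making.

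**What to change.** Replace the pain sentence in Statistical methods with one linear mixed model for repeated measures on the 30-minute, day 1, day 3 and day 7 VAS. Include arm, time, arm-by-time and baseline VAS, with unstructured within-patient covariance. Include every randomised patient with at least one post-procedure rating.

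- Name one main contrast in advance, for example the average over the four ratings, and report the arm difference with 95% CI at each time.
- Collect the 30-minute form on the day of the procedure, because the model relies on it.
- State the expected return rate, and report return by arm and day.
- Add a sensitivity analysis that shifts unreturned scores by 1 and 2 points in one arm, since the model only partly corrects loss that depends on unseen pain.
- Keep the rank test at each time as supportive.

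The cost is a methods paragraph, some programming and same-day collection of one form. No new visits, patients or data items are needed. The downside is that a 10-point score is treated as continuous, which the supportive rank tests check.

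### Age, gender and BMI are listed for analysis, but core length and procedure time are compared by a t-test that cannot use them: a possible loss of precision, not an error or a bias

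*Combined protocol and SAP*

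**What the plan says.** The protocol has no separate SAP; the analysis is set out in two short paragraphs after the description of the questionnaires.

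- The paragraph on variables for the analysis lists "Sample size, length of procedure, pain intensity before procedure and at different time points after procedure, age, gender and BMI". It does not say how any of them enters an analysis.
- Statistical methods then covers the continuous outcomes. Core length and "time taken for procedure are studied with mean, median, range and standard deviation and compared by two-sample t-test". For pain, "pain is studied with χ^2 or Mann Whitney U test or Fisher's exact test". None of these tests takes covariates, and no regression, analysis of covariance, stratified analysis or subgroup analysis is named.
- The primary endpoint under AIMS is "Assessing the quality and quantity of bone marrow core biopsies". Under Outcomes it becomes "Bone marrow core biopsy length (in mm) and artifacts assessed by the pathologist blinded for the sample", so core length is its measured, continuous part. The same list includes "Time taken by the procedure measured in seconds".
- RANDOMIZATION describes one deck: "100 cards with predestinated procedure name (50 with traditional and 50 with powered biopsy) printed on them are shuffled". Cards are drawn without replacement, and no stratification by age, gender or BMI is described.

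The documents give no significance level, power, target difference or standard deviation, and no association of age, gender or BMI with core length or time.

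**The concern.** The plan earmarks three baseline variables for the analysis and then names no method that can use them. If they predict core length or procedure time, a linear model that includes them estimates the device effect with a smaller standard error from the same patients. The number of cards is fixed at 100 and the variables are already to be collected, so any such gain would come almost free.

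The role of the variables is also left open. If adjustment was intended, the model is unwritten, and the choice between adjusted and unadjusted results could be made after the data are seen. If only description was intended, the plan does not say so.

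**Working it through.** There is no power or precision figure in the plan to reproduce, so the check works in SD units of the outcome.

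**Inputs from the documents.** 50 cards per arm, 100 in total (RANDOMIZATION); two-sample t-test (Statistical methods); three covariates: age, gender and BMI.

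**Assumptions.** Two-sided 5% level; 80% power; no dropout; share of outcome variance explained by the three covariates together (R²) from 0 to 0.30.

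**Step 1, unadjusted.** The standard error of the difference is √(2/50) = 0.200 SD. The noncentral t with 100 − 2 = 98 degrees of freedom gives 80% power at a difference of 0.566 SD. The normal approximation agrees: (1.960 + 0.842) × 0.200 = 0.560 SD.

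**Step 2, adjusted.** Two things change. The residual variance is multiplied by 1 − R². Estimating three covariates adds a cost, because chance differences in them between arms must be allowed for; the expected factor is 1 + 3/(100 − 2 − 3 − 1) = 1 + 3/94 = 1.0319. The variance multiplier is therefore (1 − R²) × 1.0319, with 100 − 5 = 95 degrees of freedom. Scaling by 1 − R² alone would overstate the gain.

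For example, at R² = 0.20 the multiplier is 0.80 × 1.0319 = 0.8255. The standard error ratio is √0.8255 = 0.909, and the equivalent number of unadjusted patients is 100/0.8255 = 121.

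| R² (assumed) | SE ratio, adjusted to unadjusted | Detectable difference at 80% power (SD) | Power at 0.566 SD | Equivalent unadjusted total N |
|---|---|---|---|---|
| 0 | 1.016 | 0.575 | 78.7% | 97 |
| 0.05 | 0.990 | 0.560 | 80.7% | 102 |
| 0.10 | 0.964 | 0.546 | 82.8% | 108 |
| 0.20 | 0.909 | 0.514 | 86.9% | 121 |
| 0.30 | 0.850 | 0.481 | 90.9% | 138 |

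**Step 3, break-even.** Adjustment neither helps nor costs when (1 − R²) × 1.0319 = 1, that is R² = 1 − 1/1.0319 = 0.031, or about 3%.

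**Step 4, check by simulation.** With 15,000 simulated trials at each R², an effect of 0.566 SD and random 50:50 allocation, the adjusted model had power 79.2, 81.2, 82.5, 87.6 and 91.0% at the five R² values in the table. The t-test had 79 to 81% throughout.

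**The case against.** The strongest reply is that an unadjusted t-test in a 1:1 randomised trial is a sound primary analysis, and that the size of any gain is unknown. Both parts stand. The documents link none of the three variables to core length or time. The background mentions osteoporosis, osteopenia and bone loss in these patients but does not connect them to age, gender or BMI. That the three are prognostic is plausible, not documented. Below about 3% of variance explained, adjustment costs a little; at 5% the gain is under one percentage point of power.

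It can also be said that the list is only an inventory of data items. It includes post-procedure pain and so is plainly not a covariate list, and age, gender and BMI may be meant for description. That reading is possible. It turns the point into one about an unstated role, which the plan should still settle.

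A reader might infer two stronger points, and neither holds.

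- *That the unstratified deck leaves chance imbalance uncorrected.* A given continuous covariate differs by more than 0.3 SD between arms with probability about 13% (0.3/0.200 = 1.5 standard errors), and at least one of three independent ones does so with probability 1 − (1 − 0.134)³, about 35%. But the t-test's standard error already allows for such differences. If three independent covariates shared R² = 0.10 equally, each would correlate √(0.10/3) = 0.18 with the outcome. A 0.3 SD imbalance in one would then shift the difference by about 0.055 SD, against a standard error of 0.200 SD. Lack of stratification is not a defect here.
- *That the plan fails to identify procedure time as an outcome.* AIMS names it as a secondary endpoint, Outcomes lists it, and the sentence just before the list of variables calls it a secondary endpoint again. The term sample size in that list is ambiguous (patients or specimen), but core length is itself listed as an outcome.

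**Conclusion.** The point holds as a possible loss of precision and an unstated role for three listed variables. It is not an error in the test, and it does not bias the comparison. Saying that precision is certainly lost would go beyond the documents, because the loss depends on an R² they do not give.

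Over the assumed range of 0 to 30%, adjustment moves the detectable difference from 0.566 SD to somewhere between 0.575 and 0.481 SD, or from 100 patients to the equivalent of 97 to 138. The gain is small at 5 to 10% and material from about 20%. The balance is lopsided in favour of adjusting: a standard error 1.6% larger if the covariates explain nothing, against 15% smaller if they explain 30%. The figures rest on the assumed 5% level, 80% power and complete data in 50 patients per arm. The change is worth making, but the trial's validity does not depend on it.

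**What to change.** In Statistical methods, make the main comparison of core length and of procedure time a linear model with arm, age, gender and BMI, with age and BMI as continuous terms. Report the adjusted difference between arms with its 95% confidence interval, and keep the two-sample t-test as a supportive analysis. State that only variables measured before the procedure may be covariates in any device comparison; this keeps procedure time and specimen measures, which the device may affect, out of the model. Say in the list of variables what sample size refers to.

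If the investigators prefer the t-test as the main analysis, the plan should at least say that age, gender and BMI are descriptive only.

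The cost is one or two sentences, no new data, three of 98 degrees of freedom, and at worst about a 1.6% larger standard error. The choice should be fixed before outcomes are compared by arm.
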